# 9.2 Immunologic Testing

Although insulin independence can be achieved via transplantation of an adequate number of viable, functional islets, a gradual reduction in the percent insulin independent patients occurs over time, with approximately 25% of patients still insulin free at 4 years post-transplant. Immune mediated islet destruction in the form of allorejection and/or recurrent autoimmunity, as well as attrition of a marginal islet mass due to exhaustion and/or toxicity of immunosuppressive agents, have all been postulated to play a role in islet loss. In order to begin to dissect the role of immune mediated reactions in allograft loss, tests will be done to determine if sensitization to donor allo- or islet autoantigens has occurred. In addition, maintenance of protective immunity in the setting of immunosuppression will be addressed, as will the role of innate immune reactions in the early post-transplant period.

While methods for determination of allo- and autoantibody have been extensively studied and are fairly well-established, reliable, reproducible and validated methods for assessment of T cell immunoreactivity to allo and/or autoantigens do not exist. For the most part, these techniques are time-consuming, technically demanding and require large blood volumes and significant staff time for set up and analysis of the resultant data. Several methods are undergoing testing in multiple T1D consortia (e.g., ELISPOT, tetramer staining, T cell proliferation assays) to determine which tests provide the most reliable data with regards to distinguishing between patients with T1D vs normal controls (for autoantigen) and to improve techniques for assessing recipient anti-donor reactivity.

## 9.2.1 Immune Assays

#### 9.2.1.1 HLA typing of donors and recipients, crossmatching

HLA typing of donors and recipients, as well as crossmatching, will be done at individual centers. A negative crossmatch is required in order for transplantation to occur.

#### 9.2.1.2 Alloantibody

Development of alloantibody is generally associated with longer term graft loss. Each sample will be tested using flow PRA screening beads to determine the presence of class I or class II antibodies. If results are negative for class 1 and class 2 antibodies, no further HLA antibody testing will be performed on that sample. If results are positive for class 1 and/or class 2, flow specificity beads will be used to determine the PRA and specificities of anti-HLA antibodies present. If antibody specificity cannot be defined using this technique, single antigen beads may be tested. Serum samples will be stored in the laboratory in the event that additional testing is

required. [name] at the University of Pennsylvania will provide core laboratory services for alloantibody analysis. Two mL blood samples for collection of serum will be obtained prior to initiation of immune suppression and transplant and at 3, 6, 9, and 12 months post-infusion, including 365 days post-initial transplant. Quarterly sample collection will continue for the duration of follow-up.

## 9.2.1.3 Autoantibody

The role of autoantibody in graft loss remains unclear. [name]'s lab in Denver will provide core lab service for autoantibody assessments.

# 9.2.1.4 Measures of innate immunity

In order to correlate expression of pro-inflammatory or pro-coagulant markers on islets with recipient response in the early post-transplant period, ethylenediaminetetraacetic acid (EDTA) anti-coagulated blood will be collected for assessment of thrombin-antithrombin (TAT), C3a, and c-peptide levels.

## 9.2.1.5 Archived serum, cells and RNA

In order to ensure that we will ultimately gain as much information as possible from these trials, and due to the ongoing development of assays such as T cell assays. Serum, cells and RNA will be archived for future analyses. Details for subjects regarding the archiving of samples and use for future assays are contained in the study's informed consent form. Subjects will have the option of whether or not they want to have samples archived and will indicate their choice on the informed consent form. A subject's choice regarding archiving samples will not affect his/her participation in the study.

Serum: Blood will be collected obtain serum, and archived in the NIDDK repository.

Peripheral Blood Mononuclar Cell (PBMC) and Plasma: Blood will be collected to obtain recipient PBMC, processed and archived in the NIDDK repository.

RNA: Blood will be collected for RNA isolation and archival in the NIDDK repository.

### 9.2.1.6 Alloimmunization Studies

HLA antibody analysis will be performed in the laboratory of [name] at the University of Pennsylvania using Luminex (One Lambda, Inc. [name]).

Subjects will be screened for anti-HLA class I/II antibodies using Luminex screening assays (LS1 and LS2). If either assay is positive, a Luminex Single Antigen (LSA) assay will be performed to define PRA antigen specificity. A Luminex Specificity Bead (LSB) assay will be performed only if LSA results are not definitive. LSA and LSB assays include the following:

CIT-05

- LSA1- high definition class I screening for specificity
- LSB1- class I screening for specificity
- LSA2- high definition class II screening for specificity
- LSB2- class II screening for specificity

# 9.2.2 University of Pennsylvania Specific Assays

Additional assays that are being developed at individual centers will be performed at those sites. Protocols and results will be shared to determine if an assay is gaining validity as a measure that should be incorporated into future trials.

# 9.2.2.1 Flow Cytometry

Basic immunophenotyping is especially important for monitoring of immunotherapies that involve agents that delete and/or alter the function of specific leukocyte subsets (e.g., T or B cells). The four-color panel that will be used for the routine evaluation of lymphocyte subsets at Penn is shown below

In brief, samples for routine flow cytometry are processed as follows: All samples are processed within 24 hours of the blood draw and usually within 4 hours. Briefly, 150 microliters of anticoagulated whole blood (sodium EDTA, equilibrated for a minimum of 30 minutes at room temperature with gentle mixing) are aliquoted in Beckton Dickinson FACS tubes. The cells are washed three times, incubated with blocking antibody (if required) and subsequently with extracellularly staining antibodies. Red blood cells are lysed and the white cells are resuspended in a buffer containing 1% paraformaldehyde. Samples are analyzed by flow cytometry within 24 hours of processing and staining.

Table 5: Four Color Lymphocyte Immunophenotyping Panel

Tube	Description	Acquisition Gate	FITC	PE	PerCP	APC
1-5	Setup and Compensation		CD8 (2)	CD8 (3) (10u)	CD8 (4)	CD8 (5)
6	Control	Lymphocytes (10K)	IgG1	IgG1	CD4	CD8
7	Immature	CD19+ Ly (10K or ET)	CD24	CD138	CD19	Class II
8*	Transitional	CD19+ Ly (10K or ET)	IgM	CD23	CD19	CD21
9	Transitional	CD19+ Ly (10K or ET)	CD10	CD38	CD19	CD27 (5ul)
10	Transitional	CD19+ Ly (10K or ET)	CD24	CD38	CD19	CD27 (5ul)
11*	Marginal/Isotype	CD19+ Ly (10K or ET)	IgD	CD24 (5ul)	CD19	IgM
12	B1	CD19+ Ly (10K or ET)	CD24	CD38	CD19	CD5
13*	MBL/Lymphoma	CD19+ Ly (10K or ET)	CD10	CD23	CD19	CD5

14*	Light Chains	CD19+ Ly (10K or ET)	Kappa	Lambda	CD19	CD5
15*	Activated/Plasmablast	CD19+ Ly (10K or ET)	CD27	CD38	CD19	CD23(20ul)
16*	Memory	CD19+ Ly (10K or ET)	IgM	CD38	CD19	CD27 (5ul)
17*	Plasma	CD19+ Ly (10K or ET)	Kappa/ Lambda	CD138	CD20	CD19 (5ul)
18	T cell	CD3+ Ly (10K or ET)			CD4	CD45
19	CD4	CD3+ Ly (10K or ET)	CD3	CD62L	CD4	CD45RA
20	CD8	CD3+ Ly (10K or ET)	CD3	CD62L	CD8	CD45RA
21*	Treg	CD3+ Ly (20K or ET)	CD3	CD127	CD4	CD25
22	T activation	CD3+ Ly (10K or ET)	CD28	CD62L	CD4	CD3
23	T activation	CD3+ Ly (10K or ET)	CD28	CD95	CD4	CD8
24	NK cells	Lymphocytes (50K)	CD3	CD56	CD8	CD16
25*	NK activation	Lymphocytes (50K)	NKG2d	CD56	CD3	NKp44(15ul)
26*	NK clones	Lymphocytes (50K)	CD158b	CD158a	CD3	NKB1 (10ul)

### *Notes (Table 5):*

All antibodies are commercially available from BD Pharmingen, Biolegend, and e-Bioscience. The minimum numbers of gated events to be collected are indicated in parentheses. In the acquisition gate column, "Lymph" or Ly means lymphocyte gate, ET means entire tube. Blocking antibodies are added to the starred tubes.  $20~\mu L$  of of each fluorophore-conjugated antibody are added per tube except to tubes in which microliter amounts of antibody added are indicated in values in parentheses. These amounts are based either on titration experiments performed in pilot experiments or manufacturer recommendations (data not shown).

# **9.2.2.2** High Definition Flow Cytometry

In addition to basic phenotyping, more detailed analysis of B cell phenotype and repertoire has been developed. The ultimate goal of these studies will be to improve monitoring of autoreactive B cells in T1D patients. These studies will assist in achieving the following aims:

- 1. Better definition of transitional B cell subsets in humans.
- 2. Analysis of peripheral lymphocyte dynamics in humans. The serial analysis of B cell depletion and repletion following rituximab therapy will provide insights into the turnover and dynamics of different peripheral B cell subsets. Plasma cells and other cells that may be resistant to B cell depletion are of special interest in this study as well.

3. Provide a technical platform for attempting to isolate and characterize (auto) antigen-specific B cells. The frequency of antigen-specific B cells to a conventional T dependent protein antigen ranges from one in ten thousand to less than one in a million lymphocytes. Therefore any method that is used to characterize these cells must be very stringent about separating these cells from the background.

To begin to address these questions, we have developed high definition (HiD) flow cytometry panels (Table 6). Key elements of the panel include the ability to remove unwanted populations of irrelevant cells types through the use of a dump channel and rigorous gating for doublet exclusion as well as live-dead cell discrimination.

Table 6: Ten Color HiD Flow Panel

Tube	FITC	PE	PE- TR/	PerCP	PE- Cy7	AF-750	APC	APC- Cy5.5/	PE- Cy5	PE- Cy5.	Pacific Blue	Live
			PE- AF610					AF-700		5		
1	No											
	stain											
2	CD8 (20ul)											
3	(2001)	CD8 (3ul)										
4			CD4 (1ul)									
5				CD20 (20ul)								
6					CD19 (1ul)							
7						CD3 (5ul)						
8							CD8 (20ul)					
9								CD38 (5ul)				
10									CD21 (20ul)			
11										CD5 (5ul)		
12											CD8 (10ul)	
13 *	IgM (20ul)	CD10 (20ul)	CD24 (5ul)	CD20 (20ul)	CD19 (1ul)	CD27 - (20ul)	CD23 (20ul)	CD38 (5ul)		CD5 (5ul)	Dump 1	Dapi
14 *	IgM (20ul)	IgD (1ul)	CD24 (5ul)	CD20 (20ul)	CD19 (1ul)	CD27 - (20ul)	CD23 (20ul)	CD38 (5ul)	CD21 (20ul)		Dump 1	Dapi
15 *	λ (20ul)	κ (20ul)	CD24 (5ul)	CD20 (20ul)	CD19 (1ul)	CD27 - (20ul)	CD23 (20ul)	CD38 (5ul)	CD138 (10ul)		Dump 1	Dapi
16 *	IgD (20ul)	Kappa (20ul)		9G4 (1ul)	CD19 (1ul)	CD27 - (20ul)	IgM (20ul)	CD38 (5ul)		CD5 (5ul)	Dump 1	Dapi
17 *	IgM (20ul)	CD267 (20ul)			CD19 (1ul)	CD27 - (20ul)	CD23 (201)	CD38 (5ul)	CD95 (20ul)		Dump 1	Dapi
18 *	NKG2 D (20ul)	CD8 (3ul)	CD4 (1ul)	CD45 (20ul)	CD16 (1ul)	CD3 (5ul)	NKp44 (10 ul)	CD56 (15ul)	CD62L (20ul)		Dump 2	Dapi

Dump 1 - CD3 (10ul), CD8 (10ul), CD14 (10ul)

Dump 2 - CD19 (5ul)

Abbreviations for table 6 are the same as in table 5. Single color controls are used for digital compensation. Flow cytometry data are acquired on an LSRII flow cytometer and analyzed using

FlowJo (Treestar Inc.) software. Four-color and ten-color immunophenotyping studies will be performed in [name] laboratory.

# 9.2.2.3 CDR3 Spectratyping, Clone tracking, and Light Chain Receptor Editing

Heavy chain spectratyping will be performed using "global" primers (FR3 +  $J_H$  cocktail) to screen for clonal expansions. Candidate expanded clones will be sequenced and  $V_H/J_H$ -specific primer sets which will be used to track specific clones in individual subjects.  $V_H/J_H$  primer sets will also be used for reading frame analysis and size distribution analysis to gain further insights into the stringency of B cell repertoire selection. Light chain receptor editing frequency will be monitored by iRS-RS quantitative PCR and diversity of editing products will be monitored in parallel by spectratyping. Results will be normalized for the amount of input DNA by actin PCR and absolute quantification will be performed using titrations of a cloned iRS-RS rearrangement into genomic DNA lacking antibody gene rearrangements (standard curve). Rearrangement diversity and frequency estimates will be normalized for the B cell fraction and kappa/lambda ratio (these measurements will be obtained from the immunophenotyping studies). CDR3 spectratyping, clone tracking and quantitative PCR assays will be performed in the [name] laboratory.

# 9.2.2.4 B and T Lymphocyte Functional Assays

B lymphocytes will be monitored periodically for functional competence to respond to light chain Fab, CpG and Fab + CpG stimulation. Mononuclear cell preparations from peripheral blood of study subjects will be frozen and tested in batches in the same assay on the same day. LPS will be included as a positive control and media will be included as a negative control. B cell activation will be monitored by calcium flux, lymphocyte activation marker expression and cell proliferation (CFSE peaks will be evaluated using ModFit software). These assays will be performed in the laboratory of [name].

T cells will be stimulated in culture with islet-derived peptides from GAD65, IAA, and IA-2. Mononuclear cell preparations from peripheral blood of study subjects will be frozen and tested in batches in the same assay on the same day. Controls include media alone, concanavalin stimulation, PMA/ionomycin and tetanus toxoid. Assay read-outs will include cell proliferation (monitored by CFSE dilution) and expression of cytokines (IL-10, TNF $\alpha$  and IFN $\gamma$ ) by ELISpot assay. These assays will be performed in the laboratory of [name].

#### 9.2.2.5 Monitoring of Rituximab

Also relevant to treatment with antibodies, chimeric molecules or other proteins is analysis for development of antibodies to the therapeutic protein; such a response can limit the efficacy of the treatment. Rituximab levels will be monitored by PK assays and the development of anti-rituximab antibodies (human anti-chimeric antibodies [HACAs]) will be monitored using the same assays that are currently in place for other rituximab trials on campus. The tests will be performed by Genentech.

# 9.2.2.6 Antibody repertoire

We hypothesize that the B cell repertoire in T1D patients will contain expanded clones and have evidence of increased receptor editing. We have developed a series of antibody gene rearrangement assays to test these assertions including CDR3 spectratyping with global and VHgene specific primers and a new kind of L chain assay that monitors the diversity of RS recombination events. We predict that CDR3 spectratyping will reveal the reproducible presence of rearrangements of particular sizes, suggestive of clonal expansion. Clonal expansion can be confirmed by DNA sequence analysis. If no evidence of clonal expansion is obtained with "global" VH primers, we will survey specific VH gene rearrangements. Of particular interest in this connection is the autoimmune-associated V gene 4-34. This H chain is found at increased frequency in a variety of autoimmune conditions and is associated with multireactivity. Furthermore, a monoclonal antibody, 9G4, can be used to isolate B cells that express VH 4-34 H chains. If expanded clones are recovered, we can monitor their longevity/turnover in the setting of B depletion therapy using clone-specific PCR assays. For receptor editing, we anticipate seeing VH gene rearrangements with increased CDR3 length, suggestive of reiterative H chain rearrangement (this can be verified by DNA sequence analysis). We also expect, if receptor editing is increased, to see a greater level of RS junctional diversity in B cells from T1D patients compared to non-autoimmune controls. It will be interesting to analyze these features of the B cell repertoire before and after B cell depletion. Drawing from our experience in B cell repertoire analysis in normal and auto-immune prone strains of mice, we look forward to applying these assays alone or in conjunction with B cell separation methods to analyze B lymphocyte repertoire in T1D patients.

## 9.2.2.7 T cell ELISpot Assays

T cell responses will be monitored by ELISpot assay. A screening assay will use dominant T cell epitopes against GAD65, IAA and IA-2 using IFN-g and TGFb secretion as read-outs. If the screening ELISpot is positive, the specificity of reacting T cells (checked against a panel of peptides) will be profiled and the secretion of multiple cytokines will be monitored. A multiplex cytokine assay is currently under development.

# 9.2.2.8 Protective Immunity

Determining whether or not protective immunity is maintained in immunosuppressed patients is important for understanding the risks associated with various agents. We will monitor the memory response to influenza virus by serology, B and T cell ELISpot and, if available, B cell flow cytometry in patients at baseline and 6 months after islet transplantation. Cell proliferation and cytokine profiling will help evaluate the nature of the immune response. Functional assays of antigen-specific B cells and T cells to influenza are in development.

### 10. STATISTICAL CONSIDERATIONS AND ANALYTICAL PLAN

## 10.1 Statistical Analyses

The goal of this study is to provide strong scientific evidence that the rate of favorable outcome in transplanted subjects is high enough to justify the risks of the procedure and the immunosuppression. All efficacy analyses will be based on the intention-to-treat principle. Once a subject has been transplanted s/he will be included in the final analysis. All transplanted subjects will also be included in the safety analysis. There will be planned interim analyses for safety and efficacy at the direction of the DSMB. Details of all statistical analyses will be given in the formal statistical analysis plan (SAP).

# 10.2 Study Endpoint Assessment

# 10.2.1 Primary Endpoint

The primary objective of the analysis is to estimate the rate of insulin independence at 75 days after the first Islet Transplant among those in the study. The primary endpoint is insulin independence (yes/no) at day 75 after Islet Transplant as defined in section 3.1. The primary analysis will compute an exact binomial estimate and a 95% confidence interval for the true rate.

The primary endpoint should be available for all randomized subjects. An exception will be if a death occurs or if the subject withdraws consent to be followed, in these cases the endpoint will be classified as failure to achieve insulin independence. Should the endpoint not be evaluated for a particular individual for other reasons, a failure will be imputed unless an evaluation is done at a time longer than 75 days after transplant and before an additional islet transplant, in which case that later value will be imputed. All imputations will be reported with the primary analysis.

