Transplantation of isolated pancreatic islets offers the distinct advantage over whole organ pancreas transplantation that it can be accomplished without a major surgical operation. Consequently, isolated islet transplantation is a much safer treatment, and so may be considered as an option for patients before the development of irreversible diabetic complications. But until recently, <10% of islet transplant recipients experienced insulin-independence after one year, in contrast to the  $\sim80\%$  of pancreas transplant recipients. The lower rate of insulin-independence following islet transplantation was attributed to a low engrafted islet mass combined with a high metabolic demand imposed by the glucocorticoids used as part of the immunosuppression. Accordingly, the islet transplant group from Edmonton initiated a protocol where islets isolated

from two or more donor pancreases were transplanted under a glucocorticoid-free immunotherapy regimen.

In the year 2000, the initial report of success with the "Edmonton protocol" represented a major advance in the field of clinical islet transplantation, where insulin-independent amelioration of hyper- and hypoglycemia occurred in seven consecutive T1D recipients with a median follow-up of 12 months. The immunosuppression regimen consisted of a combination of novel T lymphocyte directed induction therapy with the interleukin-2 receptor monoclonal antibody daclizumab, and maintenance therapy with the potent calcineurin-inhibitor (CNI) tacrolimus and the more recently developed agent sirolimus. The efficacy of the Edmonton approach has now been confirmed by several other centers, including our own where even single donor transplant recipients have enjoyed a high rate of initial insulin-independence. Unfortunately, we have found that despite early insulin-independent graft function, hyperglycemia gradually progresses and a second transplant is generally required to sustain an insulin-free state. Comparable loss of graft function over time has been reported from Edmonton, where insulin-independence rates have declined from 80% at one year to 10% by five years.

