The option of a **third islet transplant** under this protocol will be considered only if all of the following conditions are met:

- 1. The subject received greater than 4,000 IE/kg with the second transplant, but remains dependent on insulin for longer than one month after the second transplant.
- 2. There is evidence of partial graft function.
- 3. The CIT PIs, Site PIs, and the Steering Committee have determined that there were no relevant protocol deviations at the site.
- 4. The subject has been compliant with study monitoring and prescribed immunosuppressive therapy.
- 5. No evidence of a serious and life-threatening infection, AE, or other condition that precludes attempting an intraportal injection or continuation of the post-transplant treatment regimen.
- 6. No evidence of PTLD.
- 7. No evidence of progressive renal dysfunction, with blood creatinine rising above 2.0 mg/dL (177  $\mu$ mol/L).
- 8. No evidence of hypersensitization, allergic responses, or other potentially serious drug reactions to medications required by the protocol.
- 9. No evidence of abnormal liver ultrasound and LFTs within 1.5 times the ULN range.
- 10. PRA <50 by flow cytometry (assessment performed locally) and the alloantibody specificity not cross-reactive with antigen(s) present in the subsequent islet preparation in order to avoid unacceptable antigen(s).

Subjects who have completed 8 months of follow-up post-first transplant will no longer be eligible for additional islet transplants funded under this protocol. Subjects that do not meet the criteria for a subsequent transplant and do not have a functioning graft will enter a reduced follow-up schedule (Appendix 2).

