## 7.6 Follow-up Visits

At  $75 \pm 5$  days following each islet transplant, insulin-independence will be assessed as the primary endpoint as defined above (please see Section 3.1.1) based on one week of frequent capillary blood glucose monitoring ending with a fasting clinic visit for determination of HbA1c, fasting serum glucose and c-peptide, and serum glucose and c-peptide 90-minutes after ingestion of Boost®. This information also allows for the calculation of the  $\beta$ -score, a composite index of

islet graft function. Other self-glucose monitoring information captured at this visit will enable calculation of the Clarke and HYPO scores of hypoglycemia awareness and severity, respectively, the hypoglycemia fear survey, and the MAGE and LI scores of glycemic lability. This assessment will be repeated at 6, 9, 12, 15, 18, 21, and 24 months post-transplant.

The acute c-peptide and insulin responses to IV glucose and arginine will be performed during a two night admission to the GCRC scheduled at 3 months following each transplant, and at 12 and 24 months after the last transplant. The IV glucose test will be administered as a frequently-sampled intravenous glucose tolerance test in order to calculate insulin sensitivity ( $S_I$ ) and the disposition index (DI). The IV arginine test will be performed with glucose-potentiation in insulin-independent recipients and those taking  $\leq 0.1$  U/kg of daily insulin to optimize glycemic control in order to determine the  $\beta$ -cell secretory capacity at day 75 and at 12 months. Also at 3, 12, and 24 months, 72-hours of continuous glucose monitoring will be performed.

At 6 and 14 months post-transplant, paired hypoglycemic and euglycemic clamps will be performed one week apart, in randomized order, each after a one night admission to the GCRC.

At 12 months following the first transplant retinal photography will be performed.

Clinic visits for immunosuppression drug monitoring will occur monthly for the first two years and quarterly thereafter. Additional tests will be repeated as indicated in the timeline provided in the appendix.

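### A missing Day 75 primary outcome may be replaced by any later evaluation before the next transplant, with no latest day and no rule for choosing among several

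*Protocol*

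**What the plan says.** Section 10.2.1 of the Protocol defines the outcome at a point in time: "The primary endpoint is insulin independence (yes/no) at day 75 after Islet Transplant as defined in section 3.1". Section 3.1 and section 7.7 give that time as 75 ± 5 days.

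Section 10.2.1 then deals with missing outcomes in three steps.

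- Death or withdrawal of consent: "in these cases the endpoint will be classified as failure to achieve insulin independence".
- Any other reason: "a failure will be imputed unless an evaluation is done at a time longer than 75 days after transplant and before an additional islet transplant".
- If there is such an evaluation: "in which case that later value will be imputed".

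It adds a disclosure: "All imputations will be reported with the primary analysis".

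On the timing of later evaluations, section 7.6 says of the insulin-independence assessment: "This assessment will be repeated at 6, 9, 12, 15, 18, 21, and 24 months post-transplant". On further transplants, section 7.5.1 says: "Subjects who have completed 8 months of follow-up post-first transplant will no longer be eligible for additional islet transplants funded under this protocol". The same section considers a second transplant only for recipients who do not meet the insulin-independence criteria.

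**The concern.** The substitution clause has a lower time limit (after Day 75) and one event that closes it (another transplant). It has no upper time limit. A subject who is insulin-independent is not a candidate for another transplant, and nobody is after 8 months. For a subject who is never re-transplanted the closing event does not occur, and any result up to the end of follow-up can be entered as the Day 75 result.

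The protocol does not treat early and late status as the same thing. Section 1.1 reports that "despite early insulin-independent graft function, hyperglycemia gradually progresses". Section 10.5 warns that the Day 75 outcome need not predict longer-term outcomes. Section 3.1.1 lists insulin independence at Day 365 as a separate secondary endpoint, so one observation could serve as both the primary and that secondary result.

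Where several later results exist and disagree, the choice is left open and could be made with the results known. At stake is what the primary proportion means in a trial of 12 subjects, where one subject is visible in the estimate.

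**Working it through.** **Reproducing the plan's figure.** The interval is Clopper-Pearson with n = 12: lower = the 0.025 quantile of Beta(x, n − x + 1), upper = the 0.975 quantile of Beta(x + 1, n − x). For x = 6 this gives 0.2109 to 0.7891, matching the 0.21 to 0.79 in section 10.4.

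**How late a substitute can be.** Appendix 1 schedules HbA1c, MMTT and blood sugar records after Day 75 at Days 180, 270 and 365. The section 3.1 definition needs HbA1c and a week of capillary readings, as well as fasting glucose and c-peptide.

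- The Day 180 visit has a ± 7 day window, so its earliest day is 180 − 7 = 173.
- That is 173 − 75 = 98 days after Day 75, and 173 − 80 = 93 days after the primary window closes.
- On the nominal day the gap is 180 − 75 = 105 days. For Day 365 it is 365 − 75 = 290 days.

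**Can the closing event act?** Eligibility for a further transplant ends at 8 months. Days 270 and 365 come after that, so a subject not re-transplanted by then can no longer be excluded from substitution by this route.

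**Effect of one subject.** 1/12 = 8.3 percentage points. The 40% benchmark in section 3 corresponds to 0.40 × 12 = 4.8, that is, 5 or more successes.

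| Handling of one missing Day 75 outcome with a late success | Estimate | Exact 95% interval |
|---|---|---|
| Counted as failure | 4/12 = 33.3% | 0.099 to 0.651 |
| Late value used, as written | 5/12 = 41.7% | 0.152 to 0.723 |

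**Direction of the bias.** The protocol gives neither the number of missing outcomes nor the chance of late success, so these are assumptions: true Day 75 rate 30%, 2 of 12 missing independently of outcome, late success probability q from 0.2 to 0.8. The expected estimate is (10 × 0.30 + 2q)/12.

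- q = 0.2: 3.4/12 = 28.3%, below the true 30%.
- q = 0.8: 4.6/12 = 38.3%, above it.
- Both missing counted as failure: 3.0/12 = 25.0%.

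The chance of observing 5 or more successes is 23% at q = 0.2 and 51% at q = 0.8, against 15% if both count as failure. With 1 missing it is 25% to 39%, against 21%.

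So the late value can under- or overstate Day 75 success, but it never falls below what the default of failure would give.

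**The case against.** The clause has a sensible use. Section 7.5 has subjects in clinic weekly and then every two weeks over the first 3 months, and section 7.6 adds monthly drug-monitoring visits. A missed Day 75 assessment could be made up around Day 85, and scoring that as failure would be harsh. Imputations are also disclosed, so with 12 subjects a reader could recount them as failures. All of this stands. But the clause does not confine itself to made-up visits, and disclosure leaves the late values inside the primary estimate. A substitution window could sit in the SAP, which is not at hand. The protocol, however, states the rule itself, and states it without one.

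Several stronger readings are tempting and are not supported.

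- *The substitute would normally be at least 105 days late.* The Day 180 window allows 98 days, made-up visits may be much earlier, and the protocol gives no frequency for either.
- *The rule inflates the success rate.* It does so only against the default of failure. The later loss of function described in section 1.1 points to understating Day 75 success.
- *Crossing 40% changes the trial's conclusion.* Section 3 calls such a rate high and says further study may be considered. The primary analysis is estimation, and both intervals above contain 40%.
- *The mixing differs from that in CIT-07.* The imputation rule of CIT-07 is not shown, so this cannot be checked.

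**Conclusion.** The point holds as a defect in a stated rule. As written, section 10.2.1 allows Day 180, Day 270 or Day 365 status to count as Day 75 status in the primary estimate and does not say which later value to take. The text establishes this without any assumption about data.

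Its size depends on how many Day 75 outcomes are missing for reasons other than death or withdrawal of consent and are then evaluated late. That number may be zero. Each late success counted moves the estimate by 8.3 points relative to failure. The 4/12 to 5/12 example additionally assumes exactly four other successes. The net direction against true Day 75 status is unknown. The rule should be changed because the change is small and the primary proportion would then describe one time point.

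**What to change.** In section 10.2.1, replace the open-ended clause with three conditions.

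1. A substitute is accepted only if all section 3.1 criteria were evaluated by a stated latest day that falls before the Day 180 visit window opens (Day 173), and before any additional transplant. In practice this means a made-up Day 75 assessment.
2. If more than one evaluation qualifies, the earliest is used.
3. All other missing outcomes count as failure.

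The Day 120 visit as now scheduled cannot supply the substitute. Appendix 1 has fasting glucose and c-peptide there, but no HbA1c, MMTT or blood sugar record. Using it would require adding the missing assessments for the subject concerned.

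Also report the primary estimate and exact interval with every imputed subject counted as failure.

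The cost is one or two sentences and one sensitivity line. The primary estimate may come out slightly less favourable, because some late successes would now be failures.
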